## 11.2 Evaluations for Study Completion, Study Withdrawals, and Treatment Discontinuation

### Study Completion

A subject will be considered to have completed the study if he or she completed all assessments and procedures during the index PCI and follow-up period of 1 year for primary endpoint events. All randomized patients will have a follow-up assessment (telephone contact at 1, 6, and 12 months) to determine survival status and hospitalization data. If the subject dies during this period, the study coordinator and/or PI should make every effort to obtain details of the subject's death from the relevant hospital or subject's physicians and/or relatives. If confirmation of death is not available through these mechanisms, the study coordinator and/or PI will attempt to confirm the subject's death through a death index search.

### Study Withdrawal

If the subject is lost to follow up, every effort will be made to contact the subject and determine the reason that will then be documented, including the measures taken to follow-up. If subject withdraws or drops out of the study, the reason for withdrawal from the study is to be documented on the case report form (CRF) and in the source document. The study coordinator or investigator must attempt to document re-hospitalization data unless the subject expressly refuses to provide this information. If subjects withdraw from the main part of the study, they will be given the following options regarding future genomic research: either the DNA extracted will be retained and used as specified in the original consent form; or the subject may withdraw consent for *CYP2C19* genotyping and/or future unspecified genomic research, in which case the DNA sample will be destroyed. If the subject withdraws consent for future genomic research alone and would want to continue the main part of the study, the DNA sample will be destroyed after *CYP2C19* genotyping is performed.

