## **2. SPECIFIC AIMS AND OBJECTIVES / HYPOTHESES**

TAILOR-PCI is a prospective, randomized trial testing the hypothesis that after percutaneous coronary intervention (PCI), ticagrelor 90 mg bid is superior to clopidogrel 75 mg qd in reducing a composite endpoint of major adverse cardiovascular events (MACE), i.e. non-fatal myocardial infarction, non-fatal stroke and cardiovascular (CV) death, severe recurrent ischemia, and stent thrombosis (primary endpoints) in *CYP2C19* reduced function allele patients. Patients who undergo PCI will be randomized to a conventional therapy arm (i.e. to receive clopidogrel 75 mg once daily without prospective genotyping guidance) versus a prospective *CYP2C19* genotype-based anti-platelet therapy approach (ticagrelor 90 mg bid in *CYP2C19*\*2 or \*3 reduced function allele patients, clopidogrel 75 mg once daily in non-\*2 or -\*3 *CYP2C19* patients). Buccal swabs will be obtained for those subjects randomized to the prospective genotyping arm. All subjects will have a blood sample drawn for DNA analysis but genotyping using these DNA samples will be performed only after completion of the duration of anti-platelet therapy (i.e. after one year). In cases where the initial sample collected to analyze the DNA at the one year time point is found to be an unviable sample, the subject will be contacted and asked to provide another DNA sample via a blood sample or saliva sample. The primary endpoints will be assessed prospectively in the retrospectively identified reduced function *CYP2C19* allele patients receiving clopidogrel 75 mg once daily and compared with the prospectively identified reduced function *CYP2C19* allele group receiving ticagrelor 90 mg bid. A total of 5,270 patients will be enrolled.

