## **9. SCREENING PROCEDURES**

Subjects will be referred to the study or will be identified using the recruitment strategies outlined in section 8. The subject's clinical records will be reviewed to determine if the subject meets the entry criteria. Additional information may be collected from face to face or phone interviews with the subject and/or the subject's physician. If the subject meets entry criteria and is willing to participate, informed consent will be obtained.

The subject will have blood drawn for genotyping at the time of coronary angiography only if they are to undergo a PCI with required dual anti-platelet therapy for at least 12 months. For those subjects who are consented following PCI, blood sampling will be conducted by the phlebotomy team. Subjects will then be randomized to the conventional therapy or prospective genotyping arm. The blood samples of all subjects will be stored for genotyping to be performed at the end of 12 months after index PCI. The

subjects who are randomized to prospective genotyping will have 3 buccal swabs taken and processed for rapid genotyping and, based on the genotype, will be assigned to clopidogrel or ticagrelor.

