## 15.5 Specification of the Primary Analyses

Hypothesis 1A. The effect of genotype-guided antiplatelet therapy versus conventional care in patients with a reduced function *CYP2C19* allele will be estimated using a Cox proportional hazards regression model, with covariates including variables used for stratified randomization and other subject factors associated with MACE. The analysis will be conducted under the intention-to-treat principle, with follow-up beginning at randomization, but with genotype defined by the Taqman genotyping assay. Those whose prospectively defined genotype disagrees with their TaqMan-based genotype will nevertheless be analyzed based on the TaqMan result, which is the only result that is available in both arms. A sensitivity analysis will be done, taking into account the Spartan result. In the retrospective genotyping group, reduced function status will be determined by the TaqMan assay results at least one year after PCI. Subjects who withdraw or are lost during follow-up will be treated as censored at the date of last contact. Patients who complete follow-up at 12 months will be considered censored from that point onward. The proportional hazards assumption will be assessed visually using plots of scaled Schoenfeld residuals. A two-sided likelihood ratio test will be used to assess the significance of the partial effect of treatment; a p-value less than 0.05 will be considered statistically significant. Kaplan- Meier curves will be used to display survival free of MACE estimates over the first year of follow-up.

Hypothesis 1B. It is also important to determine the effect of genotype-guided antiplatelet therapy versus conventional care in patients with the wild type *CYP2C19* allele. In this case, both groups will be given clopidogrel, but the genotype-guided group patients and their physicians will know prospectively that they have the wild-type allele, at least based on the Spartan platform. The analysis will be done as outlined above in the LOF group, again defined by the TaqMan-based assessment of wild-type status. It is expected that the null hypothesis will prevail, but it is important to confirm that knowledge of genotype in and of itself does not have an effect on the rate of MACE events.

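### Section 11.2 lets a withdrawing subject's DNA be destroyed, with no CYP2C19 genotyping first, when only future-research consent is revoked

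*Combined protocol and SAP*

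**What the plan says.** Section 11.2 (Study Withdrawal) gives a subject who leaves the main study two options. Under the first, "either the DNA extracted will be retained and used as specified in the original consent form". Under the second, the subject withdraws consent for CYP2C19 "genotyping and/or future unspecified genomic research, in which case the DNA sample will be destroyed".

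The next sentence covers a different subject: "If the subject withdraws consent for future genomic research alone and would want to continue the main part of the study". For that subject the sample is destroyed only once CYP2C19 genotyping has been performed.

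On timing, section 9 states: "The blood samples of all subjects will be stored for genotyping to be performed at the end of 12 months after index PCI". Section 2 says that genotyping from the stored DNA "will be performed only after completion of the duration of anti-platelet therapy".

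On analysis, section 15.5 specifies intention to treat, "but with genotype defined by the Taqman genotyping assay". It adds: "Subjects who withdraw or are lost during follow-up will be treated as censored at the date of last contact". The Spartan result enters only a sensitivity analysis.

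**The concern.** The and/or in section 11.2 ties two separate consents to one consequence. A subject who leaves the study, revokes only the use of DNA for unspecified future research, and still permits CYP2C19 genotyping falls under the destruction rule. Nothing tells the laboratory to run the assay first. A subject who revokes the same consent but stays in the study gets the assay before destruction.

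The primary population is defined by TaqMan. A randomized subject without a TaqMan result cannot be assigned to Hypothesis 1A (LOF) or 1B (wild type). The follow-up before withdrawal, and any MACE in it, then has no place in either analysis. Section 11.2 also asks sites to keep seeking re-hospitalization data on subjects who withdraw, so the trial could hold an endpoint that it cannot use. Destruction cannot be undone.

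**Working it through.** This point turns on wording, so the first three steps compare the provisions. The fourth checks the size against the plan's own sample-size figures.

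**1. What section 11.2 does for each combination**

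| Main study | Consent revoked | Consequence for DNA | TaqMan result obtainable? |
|---|---|---|---|
| Leaves | None | Retained, used as consented | Yes |
| Leaves | Future research only | Destroyed; no genotyping step stated | Not if destroyed before the assay |
| Leaves | CYP2C19 genotyping, with or without future research | Destroyed | No, and consent requires this |
| Stays | Future research only | Destroyed after CYP2C19 genotyping | Yes |

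Only the second row is at issue. The first row shows that leaving the study does not by itself revoke genotyping. The two consents are separable elsewhere too: willingness to give DNA for genotyping is an inclusion criterion (6.2.1), while storage for other genomic research is optional (10.3, 16.7).

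**2. Order of events.** TaqMan is run about one year after PCI or later (sections 2, 5, 9, 10.1). A withdrawal during follow-up comes before that, so destruction without a genotyping step would normally come first. A subject whose TaqMan result already exists is unaffected.

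**3. Possible substitutes**
- Replacement sampling (sections 2, 5, 10.3) is for unviable samples and needs renewed contact, here with someone who has left.
- Spartan results exist only in the prospective arm and are used only in a sensitivity analysis (15.5).
- The Appendix C likelihood handles subjects without TaqMan, but it serves interim monitoring (15.8), not the final Cox model.
- Sections 15.1 and 15.5 give no rule for a randomized subject without a TaqMan result.

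**4. Effect on power**

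Inputs from section 15.2.2: HR 0.50, two-sided alpha 0.05, 1:1 allocation, 4.5% overall event rate, 5% drop-out.

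Reproducing Table 4 with the Freedman formula, events d = (z_alpha/2 + z_beta)² × [(1 + HR)/(1 − HR)]², where the last factor is (1.5/0.5)² = 9:
- 80% power: (1.960 + 0.842)² × 9 = 70.6, so 71 events; 71/0.045 = 1,578 (plan: 1,560)
- 85% power: 81 events; 81/0.045 = 1,800 (plan: 1,784)
- 90% power: 95 events; 95/0.045 = 2,111 (plan: 2,086)

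All three are within 1.3% of the plan. Dividing the plan's figures by 0.95 gives 1,643, 1,878 and 2,196, which match Table 4 exactly.

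Evaluable LOF subjects at 5,270 enrolled, interpolated in Table 4: 1,784 + (5,270 − 5,155) × (2,086 − 1,784)/(6,085 − 5,155) = 1,821. Expected events are 1,821 × 0.045 = 82. Power = Φ(√82/3 − 1.960) = 85.5%, against the plan's 85.8%.

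LOF subjects before drop-out: 1,821/0.95 = 1,917. Power by share excluded (the shares are assumptions):

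| LOF excluded | LOF analysed | Events | Power |
|---|---|---|---|
| 0% | 1,917 | 86.3 | 87.2% |
| 0.5% | 1,908 | 85.8 | 87.0% |
| 1% | 1,898 | 85.4 | 86.9% |
| 2% | 1,879 | 84.5 | 86.5% |
| 5% | 1,821 | 82.0 | 85.5% |

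The plan's inflation treats its 5% drop-out as complete loss, so the last row is in effect its own design case. No change to sample size follows.

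**The case against.** The strongest reply is that the affected group is narrow and the harm is inferred. Section 11.2 does not say when the DNA is destroyed, and no text says that such a subject is excluded from the analysis. The subject must leave the study, decline the retention option, revoke future research alone and still accept CYP2C19 genotyping. Whether sites ever meet that combination depends on consent and withdrawal forms that are not available here. The primary set depends on obtaining a TaqMan result in any case, and the plan already expects some unviable samples. A Spartan-based sensitivity analysis could place prospective-arm subjects.

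Most of this stands. The order of destruction and genotyping is inferred from the one-year timing and from the contrast with the next sentence, and the exclusion is inferred because no rule covers a missing TaqMan result. The reply does not remove the point: the text provides genotyping before destruction only for subjects who stay, and the conventional arm has nothing to put in place of TaqMan.

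A reader might also infer that the loss differs between arms and biases the hazard ratio, since the trial is open label and the drugs differ in tolerability. The documents do not support that step. Section 11.2 treats stopping therapy separately from leaving the study: a subject who stops for an adverse event remains in follow-up, and nothing about stopping triggers destruction of DNA. No text links arm or MACE to this consent choice.

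**Conclusion.** The gap is real but limited. As worded, section 11.2 can cause a randomized subject who still consents to CYP2C19 genotyping to lose the sample before TaqMan, which conflicts with the intention in section 15.5 to analyse withdrawn subjects as censored. LOF carriers would be lost from Hypothesis 1A and wild-type subjects from 1B. The issue is an avoidable exclusion after randomization, not sample size: even a full 5% exclusion costs about 1.7 points of power (87.2% to 85.5%), within the existing allowance.

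The number affected is not in the documents and is probably small. A reader might try to derive it from the 5% drop-out figure, but that figure does not measure this group. It includes patients lost to follow-up, who make no consent choice. Subjects who never agreed to future storage have nothing to revoke, and those who revoke CYP2C19 genotyping itself would lose the sample under any acceptable rule. Nor can a shift in the hazard ratio be obtained by subtracting events from the roughly 82 expected, because that total already excludes the 5% drop-outs.

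The conclusion assumes that sites apply section 11.2 literally and that withdrawal precedes the assay.

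**What to change.** In section 11.2, separate the two consents for subjects who leave the main study:
- If only future-research consent is withdrawn, perform TaqMan CYP2C19 genotyping and then destroy the DNA. This is the rule the next sentence already applies to subjects who continue.
- Destroy the DNA without genotyping only if consent to CYP2C19 genotyping is itself withdrawn.

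In section 15.5, state how randomized subjects without a TaqMan result are handled, and report them by arm with their events before withdrawal.

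The cost is a sentence or two in each section and, if the withdrawal form does not already record the two consents separately, one extra field. The assay is already planned for every subject in both arms (10.1), so no new laboratory work is added.

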### Treatment discontinuation

A subject may be discontinued from dual anti-platelet therapy if:

- The investigator or treating physician believes that for safety reasons (e.g. bleeding complications) it is in the best interest of the subject to stop treatment.
- The subject becomes pregnant and treating physician feels the risks of treatment outweigh the benefits.
- The subject dies.

Subjects who terminate dual anti-platelet therapy due to an adverse event should be followed to determine the outcome of the adverse event, in addition to the pre-specified follow-up assessments as above. Interruption of treatment will not be considered treatment discontinuation. If ticagrelor is discontinued prematurely in the reduced function *CYP2C19* allele patient due to intolerance and there is no contraindication for continued dual anti-platelet therapy, the patients and their physicians will be advised to substitute ticagrelor with prasugrel at 10 mg daily (5 mg in patients weighing less than 60 kg or age  $\geq$  75 years) or clopidogrel 150 mg daily.

## 11.3 Study Schedule of Assessments

Enrolled subjects will be required to complete up to 5 study visits/contacts (screening, randomization, and telephone follow-up on months 1, 6, and 12).

**Table 1. Schedule of Assessments to be performed during the study**

	Screening/Randomization V1 & 2			Treatment (Phone Interview)			EOT/Safety Endpoint
	Pre-Procedure**	Index Procedure	Post-Procedure	V3	V4	V5	
				30 Days (-2/+7 days)	6 months (+/-28 days)	12 months (+/- 28 days)	
Assessment of Eligibility	x						
Informed Consent	x						
Genotyping Survey 	x				x		
Hospitalization Intake 	x						
Medications	x		x	x	x	x	x
Vitals	x						
β-HCG Pregnancy test 2*	x						
Creatinine*	x		x				
CK/CK-MB*	x		x				
Troponin T/I*	x		x				
Angiogram/PCI procedure*		x					
Genotyping			x 			x	x 
Randomization			x				
Hospitalization Dismissal			x				
Electrocardiogram*	x		x				
Follow-up outcomes	x			x	x	x	x
Study Endpoint Events			x	x	x	x	x 
Death Event Form 							
End of Treatment						x	x 
Education Level & Computer Literacy***				x			

 Hospitalization forms to be completed for each hospitalization during study participation

 Only in women of childbearing potential (local urine or serum pregnancy test)

 Complete only if randomized to prospective genotyping

 Complete only if subject dies after randomization and before 12 month treatment phase

 Complete only if subject terminates participation prior to 12 months

 Completed for first 1,000 subjects only

\*Data only will be collected from these clinically indicated tests/procedures

\*\*If subject is screened/randomized post-procedure, these items will be collected post-procedure

[figure not shown]
\*\*\*This information will be collected once at any of these phone interviews, unless the patient has already completed these visits. Because these questions were not part of the original consent, the patient will be given the chance to opt out of these questions.

### 11.4 Digital & Extended Follow-Up Sub-Study

The research objective of the digital registry sub-study is similar to the research objective of the parent NIH funded TAILOR-PCI trial, which is to assess major adverse cardiovascular events in patients who have undergone percutaneous coronary intervention (PCI) based on their CYP2C19 genotyping status, beyond the 1 year follow up of the parent study. Our sub-study to create a registry is important for multiple reasons. The extended follow up allows for collection of a greater number of events and hence more power to test the primary hypothesis of TAILOR-PCI. The registry will inform the CV community of the real world practice of continuing dual anti-platelet therapy (DAPT) beyond 1 year post PCI. We will also be able to define the role of the CYP2C19 genotype on the clinical efficacy of clopidogrel beyond 1 year post-PCI, a variable that has not yet

been assessed in prior extended DAPT studies primarily due to the lack of CYP2C19 genotyping in those studies.

Figure 3

The primary purpose of this sub-study is to establish, by leveraging the resources and unique strengths of 2 NIH funded proposals, the TAILOR-PCI trial (U01HL 128606) and the Eureka Mobile Research Platform (EMRP) (5U2CEB021881), the TAILOR-PCI trial registry to follow subjects beyond 1 year post-PCI. The overall EMRP plan is depicted in Figure 3. We will be asking interested US and Canadian sites to refer their patients for the extended TAILOR-PCI digital follow-up study, and interested patients will be directed to enroll by digital means (Figures 4 & 5). Patients will be contacted via phone, text, email, or a letter. Within this communication, there will be a subject specific unique participant code tied to the TAILOR-PCI Subject ID and a URL link provided to type into a browser, allowing the participant to sign up for the study online. Once virtual registration is complete and subjects have provided their name, birthdate, email address, and established a Eureka password, the participants are directed to an electronic consent form. After reading the consent form, participants can choose to participate by clicking the button "I Agree to Participate" or opt out by choosing "Not Now". Next, they will see the Authorization to Release Protected Health Information – Research Form, which can be signed in a HIPAA-compliant DocuSign document that will be sent to the digital registry study team at Mayo Clinic (Figure 5). Because the subject is registered by study ID, their consent form will only be made accessible on the cloud (described in Figure 3) and to qualified and designated TAILOR-PCI digital registry personnel at Mayo Clinic. Once patients have provided electronic consent, they will be able to verify their phone number, enter a Eureka verification code, receive a text message with the Eureka App download link, and download the Eureka App to their phone (iOS and Android). Patients have the right to decline from participating in this digital registry program and then will no longer be recruited for the digital follow-up.

If patients are more than 24 months past their PCI, they will not be eligible for the digital registry. However, these patients will be contacted by phone, and with their verbal consent, they will be asked a similar set of questions asked at 1/6/12 months for one extended follow-up call. If education level and computer literacy questions were not asked previously, they will be included in this call, however the patient may choose to opt out of these questions.

Similarly, if patients are at 13-24 months past the index PCI and were not consented for the 18/24 month extended follow-up calls, these patients will be contacted by phone. With their verbal consent, they will be asked a similar set of questions asked at 1/6/12 months for extended follow-up at 18 and 24 months ( $\pm$  28 days for both calls). If education level and computer literacy questions were not asked previously, they will be included in one of these calls, however the patient may choose to opt out of these questions. If subjects were enrolled at US or Canadian sites, they may also be approached about participating in the digital registry. Subjects enrolled in Mexico or Korea will not be eligible for the digital registry, but may still participate in extended follow-up telephone calls.

If 3 unsuccessful attempts are made to contact subjects by telephone, a medical record review can be conducted to obtain follow-up information. Medical records may be reviewed beyond the initial length of study identified in the signed consent form, as a retrospective chart review. If the subject has died, the study coordinator and/or PI should make every effort to obtain details of the subject’s death from the relevant hospital or subject’s physicians and/or relatives. If confirmation of death is not available through these mechanisms, the study coordinator and/or PI will attempt to confirm the subject’s death through a death index search.

